**1. Full Title of the Study:**

**"A Prospective Comparative Study of the Effect of Video Education on Pain and Anxiety in Patients Undergoing TRUS-Guided Prostate Biopsy"**

---

**2. Purpose and Significance of the Study:**

The widespread use of PSA (Prostate-Specific Antigen) has facilitated the early detection of prostate cancer. Biopsies are performed on patients who are suspected to have prostate cancer based on elevated PSA and digital rectal examination. Transrectal ultrasound-guided prostate biopsy is the standard diagnostic procedure. The increasing use of PSA has led to a rise in the number of biopsies.

It has been reported that prostate biopsies and the diagnosis of prostate cancer cause anxiety in men. These procedures may lead to pain, anxiety, and stress.

Today, patients frequently use the internet to gather information. Watching videos of procedures before surgery via digital platforms is common. This study aims to measure the effect of watching TRUS-BX videos before and after the procedure on patients' anxiety and stress levels.

---

**3. Expected Benefits and Risks:**

If an increase in patients' anxiety and stress scores is observed, it may highlight the need for additional measures to inform patients prior to procedures. Videos could be adjusted to reduce stress, potentially making the biopsy experience more comfortable. However, patients who become overly anxious after watching such videos might delay or avoid diagnosis and treatment, as seen in psychiatric consultations. This study may also guide how digital content should be curated.

---

#### **4. Study Design:**

This is a comparative study of anxiety scores and visual analog scale (VAS) pain scores before and after the procedure. All patients are informed in the outpatient clinic about the TRUS-BX procedure after elevated PSA is detected.

The study was reviewed and finalized with the contributions of [name] [name] from the Psychiatry Department of Ankara Etilik City Hospital.

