#### **Control Group:**

Patients are given verbal information about the procedure. Then:

- VAS test is applied.
- STAI-II (Trait Anxiety) and STAI-I (State Anxiety) scales are administered pre-procedure.
- After biopsy: VAS and STAI-I are re-administered.
- No visual material is shown.

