#### **Video Group:**

Patients are given verbal information. Then:

- VAS test is applied.
- Videos about the procedure are found and watched with the patients via digital video platforms.
- STAI-II and STAI-I are administered pre-procedure.
- After biopsy: VAS and STAI-I are re-administered.

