#### **Image Group:**

Patients are given verbal information. Then:

- VAS test is applied.
- Illustrated drawings (from books) about the procedure are shown to the patients.
- STAI-II and STAI-I are administered pre-procedure.
- After biopsy: VAS and STAI-I are re-administered.

---

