## **7. Sample Size:**

No similar study was found in the literature. There are three independent groups:

- Video group,
- No visual group,
- Image group.
- Assuming an alpha ( $\alpha$ ) level of 0.05 and a beta ( $\beta$ ) level of 0.20 (power of 80%), and an effect size (Cohen's  $f$ ) of 0.40, it was calculated that approximately 26 participants per group (78 in total) would be required to detect meaningful differences between the three groups.

---

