## **9. Exclusion Criteria:**

- Organic mental disorders, dementia, depressive and anxiety disorders, PTSD, acute psychotic or bipolar disorders
- Patients with cognitive or physical impairments that prevent informed consent (e.g., blindness, moderate to severe mental retardation)
- Panic disorder diagnosis
- Patients with pre-procedure VAS  $\geq 5$ , suggestive of significant anxiety-stress disorders

---

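### The plan does not say how or by whom patients are assigned to the verbal-only, image and video groups, and it specifies neither a pre-education anxiety baseline nor an adjusted group comparison

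*Combined protocol and SAP*

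**What the plan says.** The title announces "A Prospective Comparative Study of the Effect of Video Education on Pain and Anxiety", and Section 2 states: "This study aims to measure the effect of watching TRUS-BX videos before and after the procedure on patients' anxiety and stress levels". Section 17 adds that the study asks whether videos intensify the anxiety that biopsy already causes. These are causal aims.

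Section 4 gives only a design label, "This is a comparative study of anxiety scores and visual analog scale (VAS) pain scores before and after the procedure", and then what each group receives. Section 7 says "There are three independent groups" and sets about 26 patients per group. Section 12 names the recruiting clinics and says that urology physicians carry out the assessments. It does not say who assigns patients.

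The order of steps in Section 4 is:

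- All groups: verbal information, then "VAS test is applied".
- Video group: next, "Videos about the procedure are found and watched with the patients via digital video platforms". Both STAI scales follow.
- Image group: book drawings are shown, and then "STAI-II and STAI-I are administered pre-procedure".
- Control group: both STAI scales follow the first VAS, with no visual material.
- All groups: VAS and STAI-I again after biopsy.

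Section 18 lists linear regression among many methods, without outcome, covariates or purpose. The final Statistical Analysis section compares groups by ANOVA or Kruskal-Wallis, with Bonferroni-corrected Mann-Whitney tests post hoc. Age, PSA and VAS are among the parameters in Section 11, but none is given a role as a covariate.

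**The concern.** Without a stated assignment method, a reader cannot tell whether a difference in STAI supports an effect of the video or only an association. If assignment followed clinic day, willingness to watch or how anxious a man appeared, the groups could differ in anxiety before any material was shown. Anxiety is also the outcome, so an unadjusted comparison would carry that difference into the result. It could create a video effect or hide one.

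The usual safeguard is a baseline taken before the intervention. Here the first STAI-I and the STAI-II in two of the three groups come after it, so an imbalance in anxiety can be neither detected cleanly nor corrected. The only anxiety-related measure listed before the material is the first VAS. The plan calls it a pain score, yet Section 9 treats a high value as "suggestive of significant anxiety-stress disorders" and excludes patients at 5 or above. It may capture anxiety only weakly.

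**Working it through.** **Inputs from the documents:** three groups, 26 per group (N = 78), alpha 0.05, Cohen's f = 0.40, ANOVA for the group comparison.

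**Assumptions (the documents give no imbalance):** one group differs by d = 0.3 or 0.5 SD in pre-education anxiety b, and b correlates r = 0.5 to 0.7 with the analysed score y. The model is y = r·b + √(1 − r²)·e, so the shift carried into y is r·d.

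**The plan's own figure.** With noncentrality λ = N·f² = 78 × 0.16 = 12.48 and F(2, 75), power is 88.3%. The stated 80% is already passed at N = 66 (λ = 10.56, power 81.8%). The stated 78 is thus larger than these inputs require. That is a separate matter and does not bear on assignment.

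**False positives when STAI-I at one time point is compared without adjustment.** If one of three means is shifted by s, the squared deviations sum to (2/3)s², so λ = 26 × (2/3) × s².

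| d | r | s = r·d | λ | P(p < 0.05), no true effect |
|---|---|---|---|---|
| 0.3 | 0.5 | 0.15 | 0.39 | 7.9% |
| 0.3 | 0.7 | 0.21 | 0.76 | 10.9% |
| 0.5 | 0.5 | 0.25 | 1.08 | 13.6% |
| 0.5 | 0.7 | 0.35 | 2.12 | 22.9% |

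If the whole imbalance lay in the analysed score (r = 1), the rates would be 17.8% and 43.0%. That is an upper bound for these two values of d.

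**Masking.** A one-group increase giving f = 0.40 is 0.40 × 3/√2 = 0.85 SD, with power 88.3%. If the video group starts less anxious, s is subtracted. For s = 0.15, 0.21, 0.25 and 0.35, power is 72.5%, 64.1%, 58.1% and 42.8%.

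**Change from pre- to post-biopsy STAI-I.** If the imbalance is equal at both times it cancels. The simulated false-positive rate is 4.9–5.2%.

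**What adjustment could recover** (single-time-point comparison, simulated, 40,000 studies per setting):

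- Adjusting for STAI-I taken before the material: 5.0–5.2%.
- Adjusting for a proxy correlated 0.2 to 0.5 with pre-education anxiety, as the first VAS might be: 6.7–10.4% for d = 0.3 and 9.9–21.7% for d = 0.5. At the weak end this is little better than no adjustment.

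**Power if only 13 per group can be randomised.** By ANOVA, λ = 39 × 0.16 = 6.24 on F(2, 36), power 56%. By ANCOVA with baseline correlation ρ, λ = 6.24/(1 − ρ²) on F(2, 35). For ρ = 0.5, λ = 8.32 and power is 70%. For ρ = 0.7, λ = 12.24 and power is 86%.

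**The case against.** The best defence is that this is mainly missing disclosure. The documents never claim randomisation, they call the study comparative, and a declared non-randomised comparison is legitimate. Section 17 also frames the primary endpoint as STAI before and after the procedure. Read as change, it is protected from an imbalance that is equal at both times.

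Much of this stands. The inflation figures apply only if a single time point is compared, and the plan does not say which score is. It is also fair that adjusting for a VAS-like covariate removes little. STAI-II may be a better covariate: if it correlates 0.7–0.8 with pre-education anxiety and the material does not shift it, the rate falls to about 5–7% (d = 0.3) or 6–11% (d = 0.5).

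The defence does not go far enough. Change from a STAI-I taken after the video describes what happens across the biopsy. It does not isolate what the video did to anxiety beforehand, which is part of the question in Section 17.

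Two stronger readings are tempting. A reader might infer that patients were selected by anxiety; the documents do not show this, and an unreported random allocation remains possible. A reader might also infer that no adjustment of any kind is planned; Section 18 names linear regression, so the text supports only that no adjusted group comparison is specified.

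**Conclusion.** The concern holds in this form. The supplied text gives no assignment method and no assigner, two of three groups have no anxiety scale before the material, and no covariate-adjusted comparison is specified, while the aim is causal. Followed as written, the plan cannot support a causal conclusion about the video, so more is at stake than a missing detail.

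The size is conditional. It is about 5%, hence no inflation, if change is compared and the imbalance is equal at both times. It is 8–11% or 14–23% if STAI-I at one time point is compared by unadjusted ANOVA, under an assumed 0.3 or 0.5 SD imbalance in one group and a correlation of 0.5–0.7. These figures illustrate the risk and do not estimate bias in this study. The finding of absence covers only the text supplied; the Study Design section, where the method belongs, is present and silent.

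**What to change.** **Patients still to be enrolled.** Add to Section 4: *STAI-I is completed before any visual material in all groups. Patients are then allocated 1:1:1 from a concealed computer-generated list, and STAI-I is repeated before biopsy.* Add to Section 18: *Groups are compared by ANCOVA of the repeated STAI-I, adjusted for the pre-material STAI-I, in randomised patients.*

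Cost: an amendment, an allocation list and one short extra questionnaire per patient. If only part of the sample can be randomised, that comparison is smaller. At 13 per group, power at f = 0.40 is about 56% by ANOVA, or about 70–86% by the recommended ANCOVA with a baseline correlation of 0.5–0.7.

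**Patients already enrolled.** State in Section 4: *Patients were assigned to the three groups by [method used], applied by [role].* If the method was not random, call the study a non-randomised comparison and add to Section 18: *STAI-I is compared between groups by a linear model adjusted for age, PSA and pre-material VAS. STAI-II is added in a sensitivity analysis, because two groups completed it after the material. Results are reported as associations; these covariates may remove little of any selection on anxiety.* The time point of the compared STAI-I should be named.

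This needs no new data. Its cost is a weaker causal claim. Recruitment was planned to end on 30.12.2024; if it has closed, only this second part applies.

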#### **Control Group:**

Patients are given verbal information about the procedure. Then:

- VAS test is applied.
- STAI-II (Trait Anxiety) and STAI-I (State Anxiety) scales are administered pre-procedure.
- After biopsy: VAS and STAI-I are re-administered.
- No visual material is shown.

#### **Video Group:**

Patients are given verbal information. Then:

- VAS test is applied.
- Videos about the procedure are found and watched with the patients via digital video platforms.
- STAI-II and STAI-I are administered pre-procedure.
- After biopsy: VAS and STAI-I are re-administered.

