## **17. Outcome Evaluation:**

The primary endpoint is the tabulation and statistical analysis of STAI responses before and after the procedure among different groups. The secondary endpoint is the writing and publication of the study results.

---

Previous literature has shown that prostate biopsy induces anxiety and depression. Zisman et al., in a prospective study of 211 men, found that 64% experienced decreased well-being and anxiety from the pre-biopsy period up to 30 days after. Fowler et al. showed that anxiety may persist for up to 12 months, even in patients with negative biopsy results. Our study seeks to answer whether pre-procedural videos intensify the anxiety already known to be associated with the biopsy.

---

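### No STAI score is listed before the video or drawings, and Section 17 does not say which STAI-I score is primary

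*Combined protocol and SAP*

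**What the plan says.** **Order of steps.** Section 4 gives each group a list that follows verbal information. In the Video Group the first VAS is followed by "Videos about the procedure are found and watched with the patients via digital video platforms", and the next item is "STAI-II and STAI-I are administered pre-procedure". The Image Group has the same order, with "Illustrated drawings (from books) about the procedure are shown to the patients" in place of the video. In the Control Group the first VAS is followed directly by "STAI-II (Trait Anxiety) and STAI-I (State Anxiety) scales are administered pre-procedure". All three groups repeat VAS and STAI-I, but not STAI-II, after biopsy.

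**Aim and endpoint.** Section 2 states: "This study aims to measure the effect of watching TRUS-BX videos before and after the procedure". Section 4 describes the design in similar terms: "This is a comparative study of anxiety scores and visual analog scale (VAS) pain scores before and after the procedure". Section 17 states: "The primary endpoint is the tabulation and statistical analysis of STAI responses before and after the procedure among different groups". It later gives the question as "Our study seeks to answer whether pre-procedural videos intensify the anxiety already known to be associated with the biopsy".

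**Tests.** Section 18 lists parametric and non-parametric tests, including paired ones (Wilcoxon, Friedman), without linking any to an outcome. The Statistical Analysis paragraph at the end of the document names ANOVA or Kruskal-Wallis, depending on distribution, then Bonferroni-corrected Mann-Whitney comparisons. It does not say which STAI score they apply to.

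**Allocation.** No section says how patients are assigned to the three groups.

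**The concern.** The question is whether the video changes anxiety. In the two exposed groups the score that looks like a baseline is, as listed, already a post-exposure score. Two things follow.

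First, state anxiety before exposure can be neither compared between groups nor adjusted for. The only scale listed before exposure in every group is the first VAS. Sections 4 and 11 treat it as a pain score, and the Section 9 exclusion confines it to values below 5. With no allocation method described, nothing in the plan shows that the groups started alike.

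Second, Section 17 leaves three quantities open: (i) pre-procedure STAI-I between groups, (ii) post-procedure STAI-I between groups, and (iii) the pre-to-post change compared between groups. They estimate different things. If none is named, the choice can be made after the results are seen, and (iii) could hide or reverse a real video effect.

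**Working it through.** **The plan's own figure.** Section 7 gives 26 per group (78 in total) for f = 0.40, alpha 0.05 and power 80%. One-way ANOVA (noncentral F, noncentrality N × f²) needs 22 per group, 66 in total (power 0.818). At 78 the power is 0.883. The stated number is not reproduced, but it exceeds what ANOVA needs, and this point does not depend on it.

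**Inputs.** From Section 7: three groups, 26 each, f = 0.40, alpha 0.05. Assumed, because the documents give none: STAI-I SD scaled to 1; pre/post correlation r; fraction L of the video effect that remains after biopsy; only the video group differs.

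**Effect size.** With group means 0, 0 and D, f = D√2/3, so D = 0.40 × 3/√2 = 0.849 SD.

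**What each score estimates (video minus control).**
- (i) Pre-procedure: D.
- (ii) Post-procedure: L × D.
- (iii) Change: L × D − D = (L − 1) × D. This is zero at L = 1 and negative for L < 1 when D is positive.

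The SD of a change is √(2(1 − r)), which is 1 at r = 0.5. Probability that the three-group ANOVA is significant:

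| L | (i) pre | (ii) post | (iii) change, r = 0.5 / 0.6 |
|---|---|---|---|
| 1 | 0.883 | 0.883 | 0.05 / 0.05 |
| 0.5 | 0.883 | 0.321 | 0.321 / 0.392 |
| 0 | 0.883 | 0.05 | 0.883 / 0.944 |

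Below L = 1, the difference behind a significant result in the last column has the wrong sign for the effect of the video.

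**Open choice under no effect at all.** This needs no L. Simulation with 40,000 trials per value of r:

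| r | 0.3 | 0.5 | 0.6 | 0.7 |
|---|---|---|---|---|
| any of pre, post, change significant | 0.122 | 0.127 | 0.128 | 0.123 |
| pre or post significant | 0.094 | 0.093 | 0.091 | 0.084 |

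Three independent tests would give 1 − 0.95³ = 0.143.

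**Value of a pre-exposure STAI-I.** For the video-versus-control contrast with pooled variance, the noncentrality is 0.849 × √(26/2) = 3.06; with 75 df the power is 0.855. Adjusting for a covariate that correlates r with the primary score replaces D by D/√(1 − r²), with 74 df:
- r = 0.5: 0.980, power 0.937
- r = 0.6: 1.061, power 0.965
- r = 0.7: 1.188, power 0.988

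**Exposure to imbalance.** If the groups differ by 0.25–0.5 SD in state anxiety before exposure, the unadjusted contrast shifts by r × imbalance: 0.5 × 0.25 = 0.125 SD up to 0.7 × 0.5 = 0.35 SD, or 15–41% of D. This is bias only if allocation makes the groups systematically different. Under random allocation, alpha already covers chance imbalance.

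**Sensitivity of a single contrast.** If group means are 0 (control), d (video) and 1.5d (image), f = d × √(3.25/3 − (2.5/3)²) = 0.624d, so d = 0.641 at f = 0.40. Video-versus-control power is then 63%, not 85.5%.

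**The case against.** The strongest reply is that a post-exposure comparison against an unexposed control is a legitimate design. That stands. Scores (i) and (ii) both estimate a video effect if the groups are comparable, and Section 2 extends the aim to both sides of the biopsy. A reader might infer that the study cannot estimate the video's effect without a baseline STAI. The documents do not support that; what is missing is a check on comparability and some precision.

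A reader might also infer that the plan will analyse change and so report a reversed result. No section adopts that reading. Section 17 can equally mean that both time points are compared between groups and both reported, which is ordinary multiplicity. The reversal figures therefore apply only if change is chosen, and they rest on assumed r and L.

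Nor is it right that no test is named: the closing Statistical Analysis paragraph names them. The gap is the score to which they apply.

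The order is that of a list. The items follow a lead-in implying sequence, but the control list ends with an item that is not a step, so listed after is as far as the text goes. If practice differs, Section 4 needs correcting anyway.

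Finally, STAI-II is a trait scale and a natural group descriptor. That also stands, with the caveat that it too is listed after exposure.

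**Conclusion.** The point holds in limited form: no pre-exposure STAI is listed for the video and image groups, no allocation method is described, and the primary STAI-I score is not chosen. Between-group comparison of either STAI-I score remains usable if the groups are comparable; the pre-to-post change should not be read as the video's effect.

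The false-positive rate is about 12–13% if all three scores are tested and any success is reported, and 8–9% for the two time points alone. Both figures assume normal scores, r = 0.3–0.7 and no correction across scores. The gain from a pre-exposure STAI-I (0.855 to 0.94–0.99) assumes a correlation of 0.5–0.7 and the video-only pattern at f = 0.40 with 26 per group.

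A reader might conclude that the three-group comparison sized in Section 7 must give way to a single video-versus-control contrast. It need not: that is a preference, and its power depends on the assumed pattern (63% in the alternative shown). Severity: should-fix.

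**What to change.** **(1) Section 4, for patients not yet assessed.** Give STAI-II and one STAI-I before the visual material, at the first VAS, and at the matched time in controls. Keep the STAI-I between education and biopsy. Adjust the group comparison for the pre-exposure STAI-I by ANCOVA. Cost: one extra short questionnaire, an earlier slot for STAI-II, and a possible repeat-test effect.

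**(2) Section 17.** Suggested wording: *The primary score is STAI-I measured after the education step and before biopsy. It is compared among the three groups by the tests in the Statistical Analysis paragraph or, where a pre-exposure STAI-I is available, by ANCOVA adjusting for it, followed by Bonferroni-corrected pairwise comparisons. Post-procedure STAI-I is secondary. The pre-to-post change is descriptive and is not interpreted as the effect of the video.* Cost: wording only; the sample size is unchanged. Making one video-versus-control contrast primary is optional.

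**If data collection is complete**, only (2) applies. Section 14 ends recruitment on 30.12.2024 and Section 15 closes the study on 20.05.2025, so this may be the case. The report should then say that the primary score was named after data collection and that no pre-exposure STAI exists. It should show the first VAS, age, PSA and STAI-II by group, noting that STAI-II is listed after exposure. Disclosure does not undo a choice made with the data in hand.

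Neither change replaces a description of how patients are allocated.

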#### **Image Group:**

Patients are given verbal information. Then:

- VAS test is applied.
- Illustrated drawings (from books) about the procedure are shown to the patients.
- STAI-II and STAI-I are administered pre-procedure.
- After biopsy: VAS and STAI-I are re-administered.

---

#### **5. Target Volunteer Group:**

Adult males with elevated PSA levels and planned biopsy.

---

## **6. Age Range:**

Men aged 50–80 (PSA screening typically begins at age 50 and is not routinely done after 75 unless clinically indicated).

---

